5.1 Screening Visit

Screening procedures will typically take place over two or more visits. All potential participants must provide independent written informed consent for screening before completing any other procedures. Thereafter, the order of the procedures specified below is suggested but not required, with the exception of the Risk Assessment, which must be completed prior to HIV pre-test counseling. The following procedures will initially occur as part of screening:

- Collection of demographic information
- Interviewer administered eligibility questionnaire, including DSM-IV diagnosis
- Urine collection (pregnancy and drug tests)
- Collection of locator information
- Risk Assessment (drug and sex behavior)

Screening may be discontinued after any one of the individual assessments listed above is completed if a participant is found to be ineligible; however, in order to protect the integrity of the entry criteria, staff will be careful to not reveal exact reason for ineligibility (e.g., injecting fewer than 12 times in past 28 days). HIV counseling and testing will be offered to everyone who consents for screening. Potentially eligible participants will then complete the following procedures:

- Pre-test HIV counseling
- Blood draw for the following laboratory tests:
 - o HIV testing
 - Hematology (CBC and platelet count)
 - o Hepatitis B surface antigen and hepatitis C antibody testing
 - o Blood chemistry (creatinine)
 - Liver function tests (ALT, bilirubin)

Sites will follow the HIV testing algorithm for screening included in Appendix II-A. Sites will confirm all positive or discordant rapid tests. If a positive result is obtained for one or both of the rapid tests, a Western blot (WB) or Immunofluorescent Assay (IFA) will be performed using the same sample for confirmation.

When results of the HIV rapid tests are available (approximately 20-40 minutes later for most volunteers), participants will receive HIV post-test counseling. Individuals who require confirmatory testing are not eligible for the study but will be asked to return to the clinic in about a week to receive their results; however, they may be rescreened according to protocol requirements if the Western blot result proves negative. Individuals who are confirmed to be HIV-infected will be counseled in ways to prevent the spread of the virus and will be provided with appropriate referrals. Each site will keep an updated referral list of counseling services, support groups, and treatment providers in their areas (Appendix IV). The staff will assist potential participants with getting appointments if needed, and may follow-up to see if the service was obtained.

Potential participants who are determined to be HIV-uninfected will complete the following assessments:

- Physical exam
- Targeted medical history

When laboratory results are received by the site, approximately one week after the blood draw, staff will determine if individuals meet entry criteria. If a potential participant has abnormal test results, the site clinician may conduct further testing before determining eligibility and should provide partcipants with appropriate referrals if necessary. If laboratory tests indicate an individual is eligible, s/he will be asked to return to the site to provide informed consent for enrollment and randomization after the study is thoroughly explained to him/her. Those who are not eligible will be informed that they do not meet the requirements of the study and, if necessary, will be referred for appropriate medical care.

Participants who are randomized and who are not infected with hepatitis B will be offered the hepatitis B vaccine over the course of the following year though it is not a requirement for study participation.

5.2 Enrollment/Randomization

If all laboratory and interview screening indicates that the individual is eligible, then the study will be fully explained to the volunteer and written informed consent for enrollment will be obtained after the volunteer completes a consent comprehension quiz. Participants will also be asked to complete a short evaluation survey of the quiz after signing the consent form. Female participants will be asked to provide urine for another pregnancy test to confirm that the participant is not pregnant at the time of first dosing. Locator information will be reviewed. Regardless of the number of screening visits required, final eligibility determination and randomization must be completed within 28 days from the time of the first blood draw for the HIV test. Participants will provide consent for study enrollment on or before the visit at which they are randomized.

Eligible study volunteers who have consented for participation will be sequentially randomized to one of two study arms according to procedures outlined in Section 7.4 and detailed in the SSP Manual. The effective point of enrollment is randomization (assignment of study arm).

Participants must be present at the study site for enrollment/randomization. BUP/NX will be initiated on the same day that randomization occurs. If a participant states that s/he will not be available, or if staff are not available, to begin dosing on the day the enrollment consent is signed, study staff will wait to randomize the participant. All participants in both arms will be scheduled for weekly counseling, which may begin on the day of enrollment/randomization or within approximately one week of enrollment.

5.3 Intervention Visits

Detailed BUP/NX dosing and counseling treatment procedures will be specified in the SSP Manual, the counseling manual, and the BUP/NX administration manual. Refer to Section 4.0 for detailed descriptions of each treatment arm.

5.3.1 BUP/NX Dispensing Visits

Participants will come to the study site for BUP/NX administration routinely for the appropriate number of weeks, depending on randomization assignment, as described in Section 4.3.3. Study staff will determine with the participant the optimal routine schedule and will carefully explain the procedures for drug administration. Efforts will be made to make these visits as quick and convenient as possible to minimize participant burden and maximize adherence. Dispensing visits can be combined with counseling and follow-up visits.

5.3.2 Drug and Risk-Reduction Counseling Visits

At the enrollment visit, participants will be scheduled for the 12 weekly counseling sessions as described in Section 4.1. Approximately every four weeks, participants will be asked to provide urine for drug testing during the counseling visits for the first year of enrollment. Women will have pregnancy testing approximately every four weeks during counseling visits for those in the substitution arm, and only at the fourth week and again approximately four weeks after the second detoxification if conducted for women in the detoxification arm.

5.3.3 Monthly Counseling Sessions

Monthly counseling sessions will be scheduled approximately every four weeks beginning at week 16 through week 52. Refer to Section 4.2.2 for a description of sessions. At each of these sessions, participants will be asked to update their locator information and provide urine for drug and pregnancy testing (for women in the substitution treatment arm only). Monthly counseling sessions can be combined with dispensing and follow-up visits.

5.4 Assessments during Safety Phase

As described in Section 2.3.2 and shown in Appendix I-B, the first 50 participants enrolled at each site will undergo the following examinations and laboratory tests each week during the first four weeks of study participation in addition to the other activities listed in Section 5.5:

- Interim medical history
- Symptom-directed physical exam
- Hematology (CBC and platelet count)

- Blood chemistry (creatinine)
- Liver function tests (ALT, bilirubin)
- Urine tests for drug use
- Assessment of social harms
- Acceptability assessment at week 4

5.5 Assessments During Full Study

In addition to intervention and laboratory visits, participants will be asked to come to the clinic every six months for clinical assessments including HIV testing and urine testing for opiates and other drugs. The week 24 counseling visit and the Week 26 follow-up visit may be combined into one visit to reduce participant visit burden. There should be no duplication of any laboratory test or the collection of any study information if the visits are combined. Visits will also include a behavioral assessment of HIV-related drug and sexual risk. More detailed assessments will be performed for all participants during the treatment phase of the study. The procedures for each visit are described below. Follow-up visits can be combined with monthly counseling sessions and BUP/NX dispensing visits.

ALT and bilirubin testing also will be performed at weeks 12 and 40 for all participants (in addition to tests completed at regularly scheduled follow-up visits); this blood draw will occur at the same visit as the urine test and counseling visit. Whenever clinically indicated, hepatitis B or C testing may be done by the study clinician.

Locator information will also be assessed at four-week intervals. To the extent possible, site staff will work with the participant to determine the best day of the week and time for this visit to be conducted each week (e.g., every Monday at 9 am). The counseling schedule will coincide with a BUP/NX dispensing visit, if possible, to minimize participant burden. Counseling visits may also be combined with follow-up visits.

5.5.1 26 and **52** Week Visits

These visits will include:

- Locator information update
- Symptom-directed physical exam, interim medical history
- Hematology (CBC, platelet count)
- Blood chemistry (creatinine)
- Liver function tests (ALT, bilirubin)
- Hepatitis testing (Week 26)
- Administer HBV vaccine if appropriate
- Urine testing for opiates and other drugs
- Pregnancy urine test for women in substitution arm and women in the detoxification arm who are undergoing a second induction
- Risk assessment (sex and drug use)
- Rapid HIV testing with pre- and post-test counseling
- Social harms assessment
- Intervention acceptability assessment

Note: The week 24 counseling visit and the Week 26 follow-up visit may be combined into one visit to reduce participant visit burden. There should be no duplication of any laboratory test or the collection of any study information if the visits are combined.

5.5.1.1 Second Detoxification at 26 weeks for those in the detoxification arm:

If the participant indicates s/he is still injecting heroin and is interested in a second detoxification, the eligibility questionnaire (including the DSM-IV diagnosis) will be administered *in addition to* those assessments listed in Section 5.5.1.

5.5.2 78, 104, 130, and 156 Week Visits

These visits will include:

- Locator information update
- Risk assessment (sex and drug use)
- Urine testing for opiates and other drugs
- Rapid HIV testing with pre- and post-test counseling
- Social harms assessment

5.6 Interim Visits

All participant visits to the study clinic or other contacts will be recorded in the study records. Any adverse events reported at clinic visits, procedures or tests performed will be appropriately documented on applicable case report forms and in the source documentation, according to the procedures detailed in the SSP manual. Female participants will be encouraged to come to the clinic for testing if they think they may be pregnant at any point during the study.

6.0 SAFETY MONITORING AND ADVERSE EVENT REPORTING

6.1 Safety Monitoring

The drug being used in this study (BUP/NX) is approved by the US FDA for treatment of opiate dependence, the indication for which it is being used in the study, and has an established safety profile based on experience in the US, Europe, and Australia. There is no *a priori* expectation that the safety profile will differ in the HPTN 058 study population; nonetheless, close safety monitoring is planned. In addition to clinical and laboratory safety, social harms will also be monitored closely.

A multi-tiered safety review process will be followed. The study site investigators are responsible for the initial evaluation and reporting of safety information at the participant level, and for alerting the protocol team if unexpected concerns arise. Participant safety will also be monitored through a series of routine safety data reviews by the PSRT. The PSRT will convene routinely to review clinical and laboratory data and reports of social harms generated by the SDMC. The content, format and frequency of the safety data reports will be agreed upon by the PSRT and the SDMC in advance of study implementation. In addition to the routine safety data reviews, the PSRT will participate in the decision-making regarding discontinuation and resumption of study drug.

In addition, the study will be overseen by and periodically reviewed by the NIAID DSMB. The HPTN SMC will also periodically review the study with particular emphasis on performance indicators such as accrual, retention and adherence to/acceptability of the study interventions.

6.2 Adverse Event Reporting Requirements

An adverse event (AE) is defined as any untoward medical occurrence in a clinical research participant administered an investigational product and which does not necessarily have a causal relationship with the investigational product. As such, an AE can be an unfavorable or unintended sign (including an abnormal laboratory finding, for example), symptom or disease temporally associated with the use of an investigational product, whether or not considered related to the product.

A serious adverse event (SAE) is any untoward medical occurrence that at any dose results in death, is life-threatening, requires inpatient hospitalization or prolongation of existing hospitalization, results in persistent or significant disability/incapacity, or is a congenital anomaly/birth defect (April 1996 International Conference on Harmonisation (ICH), Good Clinical Practice: Consolidated Guidance, (ICH E6). Important medical events that may not be immediately life-threatening or result in death or hospitalization but may jeopardize the patient or may require intervention to prevent one of the outcomes listed in the definition above may also be considered to be serious (October 1994 ICH guidance (E2A), Clinical Safety Data Management: Definitions and Standards for Expedited Reporting). For the purposes of this study, outpatient or inpatient hospital/medical facility admission for drug addiction treatment or rehabilitation will not be considered a SAE.

The expedited adverse event (EAE) reporting requirements and definitions for this study and the methods for expedited reporting of adverse events (AEs) to the DAIDS Regulatory Compliance Center (RCC) Safety Office are defined in "The Manual for Expedited Reporting of Adverse Events to DAIDS" (DAIDS EAE Manual), dated 6 May 2004. AEs that meet the criteria for expedited reporting to DAIDS must be reported on the DAIDS Expedited Adverse Event Reporting Form (EAE Reporting Form) and sent within 3 business days of site awareness to the DAIDS Safety Office. Both the DAIDS EAE Manual and the EAE Reporting Form are available on the RCC website: http://rcc.tech-res-intl.com and will be included in the Study Specific Procedures Manual. Contact and submission information for the DAIDS Safety Office is included in the EAE Manual, on the front page of the EAE Reporting Form (which is designed to serve as the cover page for submissions) and in the SSP Manual.

Specifically, the 'standard' level of reporting defined in the DAIDS EAE manual will be followed for the first 52 weeks of follow-up for participants in both study arms (from study enrollment until the participant completes 52 weeks of follow-up or is terminated from study participation for any reason). Conditions and illnesses identified in participants prior to randomization will be considered pre-existing conditions and will not be reported as adverse events, unless the condition worsens after randomization (increases in severity or frequency), in which case it would be reported as an AE.

The study drug in HPTN 058 is the BUP/NX combination (Suboxone), provided for 52 weeks to participants randomized to the substitution arm and, for participants randomized to the detoxification arm, up to 18 days beginning at randomization and/or within 30 days of the six month visit; therefore it is the relationship of all AEs to this product that is to be considered in determining the reporting requirements for each AE (e.g., whether the AE must be reported in an expedited manner to DAIDS).

All adverse events occurring in participants through week 52 will be graded according to the DAIDS Table for Grading the Severity of Adult and Pediatric Adverse Events, dated December 2004, which will be included in the SSP Manual and is available at the following website: http://rcc.tech-res-intl.com. All serious adverse events (SAEs), regardless of severity or relatedness, and all AEs that otherwise meet the criteria for expedited reporting to DAIDS (EAEs) occurring to participants in either study arm through week 52 will be reported on a standard AE DataFax case report form for entry into the study database. AEs that are not serious or do not otherwise meet the criteria for expedited reporting to DAIDS will be recorded in the study source documentation but will not be included in the study database. As noted above, for the purposes of this study, outpatient or inpatient hospital/medical facility admission for drug addiction treatment or rehabilitation will not be considered a serious adverse event.

There will be no active reporting of adverse events after the period specified above (52 weeks of follow-up); however, unexpected, serious adverse drug reactions must be reported if the study site staff become aware of the events on a passive basis, i.e., from publicly available information.

Information on all AEs included in the study database will be included in annual reports to the US FDA, and other applicable government and regulatory authorities. The investigators will report information on AEs and SAEs to the responsible Institutional Review Boards/Ethics Committees in the US and the host countries in accordance with applicable regulations and individual IRB/EC requirements.

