The treatment phase of the study will last for 52 weeks. A BUP/NX dose reduction period of approximately six weeks will occur between weeks 47 and 52 (inclusive) in those assigned to the substitution treatment arm. Those assigned to the detoxification arm will receive BUP/NX for a maximum of 18 days; detoxification may be repeated at 26 weeks if the participant in this arm is still injecting and meets criteria for opiate dependence (Section 4.4.1). Participants will be followed after enrollment for a minimum of 104 weeks and a maximum of 156 weeks, depending on when they are enrolled in the study. HIV testing and risk assessment will be conducted during the treatment and post treatment phases of the study. Additionally, participants in both arms will have routine urine testing for opiates and other commonly abused drugs. Safety will be assessed according to the procedures outlined in Section 6. Dosing ranges and adverse events will be reported to determine if the effects of the study drug (licensed in the US for the indication for which it is being used in the study, treatment of opiate dependence) are different in the study population than expected, based on experience in the US and Europe.

Because of the well-documented effects of buprenorphine in reducing craving and preventing withdrawal, the study will not be placebo-controlled as participants would quickly become unblinded following study drug administration. Additionally, the trial is designed to test the overall effectiveness of the HIV prevention strategy of providing BUP/NX coupled with drug- and risk-reduction counseling, as opposed to testing the efficacy of the medication as a treatment for opiate dependence. Thus, the use of placebo would be an inappropriate and costly design feature.

The study is designed to test the long-term effect of a 52-week treatment model on HIV acquisition. Past research among patients receiving methadone provides evidence that one year is the minimum amount of time required to achieve long-term sustainable changes in injection drug use risk behavior. The design will allow for the assessment of intervention effects for up to three years, both during and post-treatment. The sustainability of the intervention effects beyond the active treatment phase is a central tenet for the potential public health impact of this intervention.

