2.3.1 Safety and Feasibility Phase

The study will begin with a safety phase during which each site will enroll 50 participants over a period of approximately six months. The primary purpose of this initial phase is to collect detailed safety data that will be made available to the sponsor and the appropriate oversight and regulatory authorities in Thailand, China, and the US, as needed. In addition, the feasibility and acceptability data on the first 50 participants in the study at each site will allow the sites to carefully plan for and establish appropriate full study operations, including procedures for study drug administration and monitoring.

The safety and feasibility phase will follow the same design as the full study, including 1:1 randomization, study drug administration, and counseling, but it will include a more intensive evaluation schedule for the first four weeks of an individual's participation in the study. For this initial phase, potential volunteers will be asked to sign a separate informed consent form that explains the additional evaluation requirements during the first four weeks of the study.

Evaluation of the initial safety and feasibility phase data will occur in two stages. The first stage will be site-specific (with available data from the two China sites likely combined) to be conducted after the 50th participant enrolled at each site completes four weeks of follow-up. The second stage will include data from all 150 safety and feasibility phase participants, in addition to other safety data accumulated up to that point, across all sites once the last participant enrolled completes four weeks of follow-up. The Statistical and Data Management Center (SDMC) will prepare comprehensive data summaries for each of the site-specific evaluations and the blinded interim evaluation for review by the Protocol Safety Review Team (PSRT) and at least one representative of the HPTN Study Monitoring Committee (SMC). The reviews will focus on both clinical and laboratory safety data and trial feasibility indicators such as screening, accrual, retention, and adherence to and acceptability of the study drug and

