2.3.2 Assessments during the Safety and Feasibility Phase

Participants in the safety and feasibility phase will follow all procedures and undergo all assessments as specified for the full study in Section 5.0. In addition, after enrollment, the clinical and laboratory evaluations listed below will be conducted every week for the first four weeks for participants in both study arms. Evaluation of participants in the detoxification arm will allow for comparison with those in the substitution treatment arm and will minimize differences in contact and attention between the two groups.

The following assessments will be employed:

- Interim medical history
- Symptom-directed physical exam
- Hemotology (Complete Blood Count [CBC] and platelet count)
- Blood chemistry (creatinine)
- Liver function tests (ALT, bilirubin)
- Urine tests for drug use
- Assessment of social harms
- Acceptability assessment at week 4

Management, reporting and review of adverse events and social harms will follow the procedures specified for the full study in Section 6.0.

Each participant will complete an intervention acceptability assessment at the completion of the fourth week of the study. Study staff not involved in delivery of the counseling or drug intervention components will administer these assessments.

Adherence to the intervention components will be measured by participants' completion of the individual counseling sessions and drug dispensing visits as scheduled during the first four weeks of the study.

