7.3 Evaluation of Safety Phase

In a cohort of size 50, the following table presents the probabilities that 1 or more, 3 or more, 5 or more, or 10 or more subjects will experience adverse events at different underlying (true) event rates. For example, if the underlying rate of an adverse event is 10%, then there is a 57% chance that an event rate of 10% or higher will be observed (5 or more events). Likewise, if the true adverse event rate is 30% and 20% is the maximum acceptable adverse event rate for the intervention, there is a 4% (1 – 0.96) chance that there would be an inadequate number of events to conclude that the intervention has an unacceptable level of harm.

True Event	P(1 or more events,	P(3 or more events,	P(5 or more events,	P(10 or more events,
rate	n=50)	n=50)	n=50)	n=50)
1%	0.39	0.01	0.00	0.00
2%	0.64	0.08	0.00	0.00
5%	0.92	0.46	0.10	0.00
10%	0.99	0.89	0.57	0.03
20%	1.00	1.00	0.98	0.56
30%	1.00	1.00	1.00	0.96

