APPENDIX VI: HPTN 058 Adverse Event Reporting and Documentation Requirements*

	Adverse Event	RELATIONSHIP TO STUDY PRODUCT	Record event and grade in primary source documents	AE LOG (DataFax to SDMC)	EAE FORM (to DAIDS RCC within 3 business days of site awareness)
	Results in Death	Regardless of relationship	YES	YES	YES
	Results in persistent or significant disability or incapacity	Regardless of relationship	YES	YES	YES
	Is a congenital anomaly or birth defect or fetal loss	Regardless of relationship	YES	YES	YES
Serious Adverse Events	Requires or prolongs hospitalization	Probably not related Possibly related Probably related Definitely related	YES	YES	YES (if meets one of the relationship criteria)
	Requires intervention to prevent significant incapacity/permanent disability or death	Probably not related Possibly related Probably related Definitely related	YES	YES	YES (if meets one of the relationship criteria)
	Is life-threatening (including all Grade 4 AEs)	Probably not related Possibly related Probably related Definitely related	YES	YES	YES (if meets one of the relationship criteria)
	All other SAEs	Not related to study product	YES	YES	NO (unless directly related to study participation)
Non- Serious Adverse Events	All non-serious AEs	Regardless of relationship	YES	NO	NO

^{*} All AEs must be documented in the participant's source record, regardless of seriousness, severity or relatedness. AEs will only be documented and reported to the SDMC/DAIDS as appropriate for participants in both study arms through week 52 of follow-up.

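### Non-serious, non-expedited adverse events stay out of the study database even in the safety phase, so its reviews cannot obtain rates of symptomatic drug effects from that database

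*Protocol*

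**What the plan says.** Section 6.2 sends all serious adverse events, and any others meeting the DAIDS expedited criteria, to the database through week 52: they "will be reported on a standard AE DataFax case report form for entry into the study database". Every other adverse event "will be recorded in the study source documentation but will not be included in the study database". Appendix VI has the same rule in its row "All non-serious AEs": source documents yes, AE log to the SDMC no, whatever the relationship to study product. Its serious block includes life-threatening events, and with them all Grade 4 events; these are logged.

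The safety phase has no exception. Section 2.3.2 states: "Management, reporting and review of adverse events and social harms will follow the procedures specified for the full study in Section 6.0".

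Three sections describe what the safety data are for:

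- Section 2.3.1: "The primary purpose of this initial phase is to collect detailed safety data". The SDMC prepares the summaries, and "The reviews will focus on both clinical and laboratory safety data and trial feasibility indicators".
- Section 2.3: "adverse events will be reported to determine if the effects of the study drug" differ in this population from what US and European experience would suggest.
- Section 7.3 tabulates the chance of 1, 3, 5 or 10 or more events in 50 participants at true rates of 1% to 30%. One example supposes a true rate of 30% and that "20% is the maximum acceptable adverse event rate for the intervention".

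**The concern.** The effects the protocol expects from BUP/NX are mostly symptoms. Section 1.1.5 lists sedation, drowsiness, headache, pain, sweating, nausea and constipation; section 8.3 gives a similar list. Few of these would ordinarily be serious or meet expedited criteria. Under section 6.2 the rest are recorded only at the sites, and the SDMC holds no log entry from which to count them.

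So the phase set up to gather detailed safety data would produce no database rate for the most expected kind of drug effect. The section 2.3 question would be answered for these effects only by the few events that happen to be serious or expedited. An analysis plan cannot repair this, because it cannot tabulate data that the protocol keeps out of the database.

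**Working it through.** **1. Reproduce the plan's table.** With n = 50 and true rate p, the chance of r or more events is the binomial tail P(X ≥ r) = Σ C(50,k) p^k (1−p)^(50−k), summed over k = r to 50. The two worked examples in section 7.3 give:

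- p = 0.10, r = 5: 0.5688 (printed 0.57)
- p = 0.30, r = 10: 0.9598 (printed 0.96)

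All 24 cells agree within 0.02. The largest visible difference is p = 0.10, r = 10: 0.0245 against a printed 0.03. The table is sound, on the premise that every event of the type is counted.

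**2. Apply the database rule.** Let s be the share of a given symptomatic event type that is serious or expedited and so reaches the database. If each affected participant's event is recorded independently with probability s, the recorded count is binomial with n = 50 and rate q = p × s. The protocol gives no value for s, so it is an assumption, shown over a range.

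| s (assumed) | q at p = 0.30 | Expected recorded (50q) | P(10 or more) | q at p = 0.10 | Expected recorded (50q) | P(5 or more) |
|---|---|---|---|---|---|---|
| 100% | 0.30 | 15 | 0.9598 | 0.10 | 5 | 0.5688 |
| 50% | 0.15 | 7.5 | 0.2089 | 0.05 | 2.5 | 0.1036 |
| 20% | 0.06 | 3 | 0.0007 | 0.02 | 1 | 0.0032 |
| 10% | 0.03 | 1.5 | <0.0001 | 0.01 | 0.5 | 0.0001 |
| 5% | 0.015 | 0.75 | <0.0001 | 0.005 | 0.25 | <0.0001 |

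The right-hand columns can be partly checked against the plan's own table. A 10% effect recorded half the time behaves like its 5% row (0.10 for 5 or more). Recorded one time in five or one in ten, it behaves like its 2% or 1% row (0.00 for both).

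**3. What the rule leaves visible.** Section 6.2 counts an abnormal laboratory finding as a possible adverse event. Section 2.3.2 requires CBC, platelets, creatinine, ALT and bilirubin weekly for four weeks, and section 2.3.1 includes laboratory safety data in the reviews. For laboratory abnormalities s is in effect 100%, and the section 7.3 probabilities apply as printed.

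**The case against.** The rule is deliberate and consistent across sections 2.3.2 and 6.2 and Appendix VI. Section 6.1 gives the context: an approved drug, used for its approved indication, with an established safety profile and no prior expectation of a difference. Every event is still graded and kept in source, sites must alert the protocol team to unexpected concerns, and the primary endpoint of HIV infection or death is untouched. All of that stands. It supports lean collection in the full study and limits how serious the point is. It explains less well why a phase meant for detailed safety data has the same rule.

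It may also be said that section 5.6 puts adverse events on applicable case report forms, and that section 6.1 leaves the content of safety reports to be agreed before the study starts. Neither restores the data: section 6.2 and Appendix VI define which events go on the form, and a report cannot count what the database excludes.

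Several stronger readings are tempting, and the protocol does not support them:

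- *The reviews would see only serious events and laboratory values.* Section 2.3.1 promises comprehensive summaries of clinical and laboratory data, with adherence and acceptability. Nothing limits them to the AE log.
- *Events of every grade are withheld.* Grade 4 events are logged under Appendix VI.
- *The 5-or-more and 10-or-more columns of section 7.3 cannot operate.* They can, for laboratory abnormalities.
- *Section 7.3 sizes the phase and sets a 20% stopping limit.* It illustrates probabilities for a fixed group of 50, and the 20% is a hypothetical in an example. No decision rule is defeated.

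**Conclusion.** The point holds for symptomatic adverse events that are neither serious nor expedited. Their rates cannot be obtained from the study database for the site reviews, the 150-participant review or the comparison in section 2.3, and for these events the section 7.3 probabilities do not describe what reviewers would see. At a true 30% rate the chance of 10 or more recorded events in 50 is 0.0007 or less if 5–20% are serious or expedited, and 0.21 if 50% are, against a printed 0.96.

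That no log entry reaches the SDMC follows from the text alone. The size of the loss rests on the assumed share and on independent recording. This is an inexpensive improvement to safety review, not a threat to the efficacy conclusion.

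**What to change.** In sections 2.3.2 and 6.2 and Appendix VI, require that for the first 50 participants at each site, in both arms, all adverse events (or Grade 2 and above, if volume is a concern) with onset from randomization through week 4 go on the AE log with grade and relationship and are sent to the SDMC. Keep the serious-and-expedited rule after that.

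Tabulate these events pooled across arms for the PSRT and Study Monitoring Committee, because section 2.3.1 describes the interim evaluation as blinded and reserves unblinded review for the DSMB. By-arm tables should go to the DSMB only. They will be a weak test of drug effect, since the detoxification arm also receives BUP/NX for up to 18 of the 28 days.

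Reconcile sections 2.3, 5.6 and 7.3 with the new rule. Four weeks of data will answer the section 2.3 question only in part, because substitution treatment runs to 52 weeks, and the text should say so. If the sponsor keeps the present rule, restate sections 2.3 and 7.3 as covering only serious events, expedited events and laboratory abnormalities.

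The cost is AE log pages for about 150 participants over four weeks, and their data entry. The weekly interim history and symptom-directed examination are already scheduled, and section 6.2 already calls for events to be graded, considered for relationship to study drug and kept in source. No new visit or assessment is needed.
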